#### 12.1.2 Incidence of adverse events and adverse drug reactions (summary)

The variables to be analyzed are as follows:

- AEs and ADRs

- AEs and ADRs leading to death
- Serious AEs and ADRs excluding deaths
- AEs and ADRs leading to study drug withdrawal
- AEs and ADRs leading to dose reduction
- AEs and ADRs leading to dose interruption
- AEs and ADRs of interest

The number of events, number of subjects with events, and incidence rates of events will be presented.

### **12.1.3 Occurrence of adverse events and adverse drug reactions**

The variables to be analyzed are as follows:

- AEs and ADRs
- AEs and ADRs leading to study drug withdrawal
- AEs and ADRs leading to dose reduction
- AEs and ADRs leading to dose interruption
- Serious AEs and ADRs
- AEs and ADRs of interest
- AEs and ADRs of interest leading to study drug withdrawal
- AEs and ADRs of interest leading to dose reduction
- AEs and ADRs of interest leading to dose interruption
- Serious AEs and ADRs of interest

The number of events, number of subjects with events, and incidence rates of events will be presented overall and by primary SOC and PT. For AEs and ADRs of interest, event categories will be presented instead of primary SOCs.

### **12.1.4 Severity of adverse events and adverse drug reactions**

The variables to be analyzed are as follows:

- AEs and ADRs
- AEs and ADRs of interest

The number of events by severity will be presented overall and by primary SOC and PT. The number of subjects with events and incidence rates by severity will be presented overall and by primary SOC and PT. For multiple events of the same category occurring in a single subject, only the event with the highest severity will be considered in the calculation of the number of subjects with events and incidence rates.

For AEs and ADRs of interest, event categories will be presented instead of primary SOCs.

### **12.1.5 Early occurrence of adverse events and adverse drug reactions**

Applicable period: Period I, R788 treatment period

The variables to be analyzed are as follows:

- AEs and ADRs occurring up to Week 4 (Day 29)
- AEs and ADRs of interest occurring up to Week 4 (Day 29)
- AEs and ADRs occurring up to Week 12 (Day 85)
- AEs and ADRs of interest occurring up to Week 12 (Day 85)

The number of events, number of subjects with events, and incidence rates of events will be presented overall and by primary SOC and PT.

For AEs and ADRs of interest, event categories will be presented instead of primary SOCs.

### **12.1.6 Timing of occurrence of adverse events and adverse drug reactions**

Applicable period: R788 treatment period

The variables to be analyzed are as follows:

- AEs and ADRs
- AEs and ADRs of interest

The categories of timing of onset are shown as follows.

- $\leq 12$ ,  $12 < \leq 24$ ,  $24 < \leq 36$ ,  $36 < \leq 48$ ,  $48 < \leq 72$ ,  $72 <$  weeks, follow-up period

For each category of timing of onset, the number of events, number of subjects with events, and incidence rates of events will be presented overall and by primary SOC and PT. The denominator for the calculation of incidence of the events occurring in the follow-up period will be the subjects who received R788, excluding the ongoing subjects.

For AEs and ADRs of interest, the event categories will be presented instead of primary SOCs.

If the same event occurred multiple times, analysis will also be conducted to include only the events of initial onset. In such cases, the first occurrence of the event within each category of timing of onset will be analyzed overall and by primary SOC and category of AEs of interest as well.

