 - The day at the beginning of study drug administration in Period II is early transition (ET) Day 1 for early transition subjects (subjects who meet all the "Transition criteria to Period II for subjects who withdraw from Period I"). Period II is defined as 28 weeks from ET Day 1 to ET Week 28.
- 4) Non-dosing period

Non-dosing period is defined as maximum 4 weeks from Week 52 or ET Week 28 to Day 1 of Period III.

5) Period III

Period III is defined as the period from Day 1 of Period III to the date of marketing approval of R788.

- 6) Follow-up period
 - Follow-up period is defined as 2 weeks from Week 52 or ET Week 28 to the tests at the end of the follow-up period for subjects who complete Period II and are not willing to participate in the Non-dosing period and Period III.
 - Follow-up period is defined as 2 weeks from the Withdrawal Visit to the tests at the end of the follow-up period for subjects who withdraw from Period I and do not transition to Period II, those who withdraw from Period II, and those who withdraw from Period III.
 - Follow-up period is defined as the period until 2 weeks after Week 52 or ET Week 28 for subjects who withdraw from the Non-dosing period before ND Week 2.
 - No follow-up period is established for subjects who withdraw from the Non-dosing period at ND Week 2 or later or subjects who continue Period III until the date of marketing approval of R788.

*: Subjects who meet all the "Transition criteria to Period II for subjects who withdraw from Period I"

Figure 1 Structure of Study

Transition:

1) Transition to Period II

The following subjects transition to Period II.

- Subjects who completed Period I
- Early transition subjects (subjects who meet all the "Transition criteria to Period II for subjects who withdraw from Period I")

- 2) Transition criteria to Period II for subjects who withdraw from Period I
 - (1) Subjects who meet any of the following criteria and withdraw from Period I due to "2) Lack of efficacy (inadequate response)" in "Withdrawal criteria (withdrawal in individual subjects)"
 - Subjects with a platelet count of ≥ 15000/μL on Day 1:
 - a) Platelet count of $< 50000/\mu L$ after Week 12 despite the increased dose to 150 mg *bid* for more than 4 weeks.
 - b) Platelet count of $< 50000/\mu$ L after Week 12 because of the inability to increase the dose to 150 mg *bid* due to possible poor tolerability.
 - Subjects with platelet count of < 15000/μL on Day 1:

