Reason: Since the non-dosing period only includes a small number of scheduled evaluation time points and includes many unscheduled measurements, evaluation at LOV that includes unscheduled measurements was added to enable a more appropriate evaluation. In addition, measurements after the use of rescue medication were presented graphically as there is a limited number of measurements on platelet count during the non-dosing period.

8) In “[11.2.4.4 Decrease in platelet count after dose interruption](#),” evaluation of the decrease in platelet count during the non-dosing period was added.

Reason: Added to evaluate the impact of dose interruption on platelet count.

9) In “[11.2.6.2 Duration of platelet response](#),” evaluation of the duration of maintenance in R788 treatment period was added. In “[11.2.6.3 Individual plots of platelet count](#),” a swimmer plot in R788 treatment period was added.

Reason: Added for evaluation including the platelet response from Period III onwards.

10) In “[6.8 Subgroup Analyses](#)” and “[11.3 Subgroup Analysis of Efficacy](#),” evaluation of platelet count for responders and non-responders in stable platelet response was added.

Reason: Evaluation methods in the research papers on overseas studies and integrated analysis were added for the detailed evaluation of differences in platelet response between responders and non-responders for stable platelet response.

11) In “[12.1.6 Timing of occurrence of adverse events and adverse drug reactions](#),” categories of the timing of onset were corrected. In addition, evaluation on the initial onset of AEs and ADRs in the multiple occurrences of the same event was added.

Reason: Period III was previously classified in an independent category; however, it was decided that categorized by the number of days from the day of first administration of R788, combined with the events that occurred in other periods. Also, this was added to evaluate the duration to the initial onset of AEs and ADRs.

12) In “[12.1.7 Occurrence of adverse events and adverse drug reactions by dose at onset](#),” evaluation of the AEs and ADRs by dose at onset was added.

Reason: Added to evaluate the impact of the dose on the onset of AEs and ADRs.

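### SAP 12.1.6 promises an initial-onset analysis but counts the first event in every time interval; its follow-up denominator can also include subjects with no follow-up period

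*SAP*

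**What the plan says.** SAP 12.1.6 applies to the R788 treatment period. It sorts events by time of onset into six intervals (up to 12 weeks, 12 to 24, 24 to 36, 36 to 48, 48 to 72, and beyond 72) plus the follow-up period, seven categories in all. For each category, "the number of events, number of subjects with events, and incidence rates of events will be presented overall and by primary SOC and PT".

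Version 3.0 added an analysis for events that occur more than once in a subject. Two adjacent sentences define it:

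- The first says that "analysis will also be conducted to include only the events of initial onset".
- The second says that "the first occurrence of the event within each category of timing of onset will be analyzed overall and by primary SOC", and also by category of adverse event of interest.

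The change log in SAP 16.3, item 11, gives the reason: "this was added to evaluate the duration to the initial onset of AEs and ADRs".

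For follow-up events, the same section says that the denominator "will be the subjects who received R788, excluding the ongoing subjects". On who has follow-up, the protocol (Synopsis, Structure of the study, item 6, and section 8.2) states: "No follow-up period is established for subjects who withdraw from the Non-dosing period at ND Week 2 or later or subjects who continue Period III". The last group means those still in Period III when R788 is approved.

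**The concern.** The two sentences on initial onset prescribe different things. An event of initial onset happens once per subject. A first occurrence within a time category can happen once per category. If the programmer follows the second sentence, a recurrence in a later interval is tabulated as an initial onset there, and the table no longer answers the question for which it was added. At the least, two programmers could build different tables from the same text.

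The follow-up denominator raises a separate, smaller issue. A subject for whom no follow-up period exists cannot contribute a follow-up event, yet the rule keeps that subject in the denominator once he or she is no longer ongoing. Any such subject lowers the reported follow-up incidence.

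**Working it through.** The plan gives no figure on this point, so there is none to reproduce. The check compares the rules and then illustrates them under stated assumptions.

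**Initial onset: an identity.** Take any level (overall, SOC or category of interest) and any interval.

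- Main timing table, subjects with events: subjects with at least one event in that interval.
- First-within-interval rule: each such subject contributes exactly one first occurrence in that interval, and no other subject contributes any.

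The two counts are therefore equal in every interval, whatever the data. The rule reduces the number of events to the number of subjects, which the main table already shows. It carries no information on whether the event had occurred in an earlier interval.

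**Example at category level.** SAP Table 5.3-1 places nausea and diarrhoea together under gastrointestinal complaints. Suppose that a subject has nausea in week 5 and diarrhoea in week 30. Under first-ever counting, the category onset falls only in the interval up to 12 weeks. Under first-within-interval counting, the subject is an onset both there and in the 24-to-36-week interval. A subject with the same event in 4 of the 6 treatment intervals gives 4 onsets instead of 1.

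**Size under an assumed recurrence rate.** The documents give no event rates. Assume the same independent chance p of the event in each of the 6 treatment intervals. Onsets per subject are then 6p under the interval rule and 1 − (1 − p)^6 under first-ever counting.

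| p | Interval rule, 6p | First-ever, 1 − (1 − p)^6 | Ratio |
|---|---|---|---|
| 0.1 | 0.60 | 1 − 0.531 = 0.47 | 1.28 |
| 0.2 | 1.20 | 1 − 0.262 = 0.74 | 1.63 |
| 0.4 | 2.40 | 1 − 0.047 = 0.95 | 2.52 |

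**Follow-up denominator: who is in it.** Subjects still in a period at the cut-off are ongoing (SAP 8.2) and are excluded. Among the rest, the protocol (Synopsis and 11.9.1) gives follow-up to:

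- those who leave Period I without moving to Period II;
- those who leave Period II;
- Period II completers who do not go on;
- those who leave the Non-dosing period before ND Week 2;
- those who leave Period III.

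Two groups have none: those who leave the Non-dosing period at ND Week 2 or later, and those who stay in Period III until approval. The second group is ongoing at the second cut-off, so it enters the denominator only if the table is rerun at study completion.

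**Follow-up denominator: size.** Let N be the non-ongoing R788 subjects and c those among them without follow-up. The reported incidence equals the incidence among subjects with follow-up multiplied by (N − c)/N. Assume N = 24, the planned total (Protocol 8.9.1) and so a ceiling under the plan, with one subject having a follow-up event. The SAP rule gives 1/24 = 4.2% in every row.

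| c | N − c | Incidence with follow-up as denominator | Factor (N − c)/N |
|---|---|---|---|
| 0 | 24 | 4.2% | 1.00 |
| 2 | 22 | 4.5% | 0.92 |
| 8 | 16 | 6.25% | 0.67 |
| 16 | 8 | 12.5% | 0.33 |

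**The case against.** The strongest reply on initial onset is that the sentence before the disputed one already prescribes an analysis of initial onsets only. The disputed sentence names the overall, SOC and category-of-interest levels, leaves out PT, and reads as an extension. On that reading, PT-level tables follow the first sentence and are correct. This stands as far as it goes. A reader might infer that the SAP cannot show initial onset at all, and the documents do not support that. The reply does not rescue the levels that the disputed sentence does name, as the nausea and diarrhoea example shows.

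On the denominator, the reply is stronger. Ongoing subjects are already removed and most of the others do have follow-up. The group left at the second cut-off is confined to late withdrawals from a period of at most 4 weeks, and it may be empty. Those subjects have also been observed off drug for about 2 weeks, and SAP 12.1 reports Non-dosing period events separately. A reader might infer that follow-up incidence will be markedly understated. That would need many Period III completers in the denominator, hence a rerun at study completion. Section 12.1.6 does not specify one; the SAP states a completion-only analysis just for Period III treatment compliance (10.3).

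It can also fairly be said that the tables are descriptive, that early events have their own table (12.1.5), and that events of interest are listed (12.6). This limits the consequence but does not remove the contradiction.

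**Conclusion.** SAP 12.1.6 contradicts itself on initial onset. At the overall, SOC and category-of-interest levels, the rule as written reproduces the subject counts of the main timing table and does not show first onset, contrary to the purpose in 16.3. That conclusion follows from the wording and needs no assumed data. The ratios of 1.28 to 2.52 do rest on assumed, equal and independent interval risks, and only illustrate how far the counts could diverge.

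The follow-up denominator is a secondary point. It can include subjects without a follow-up period, but their number is unknown. With 24 non-ongoing subjects assumed, the factor runs from 1.00 (none) to 0.33 (16 of 24), and at the second cut-off it may be at or near 1.00.

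Both points concern descriptive safety tables only; the primary analysis is untouched. Both are worth correcting because the tables are small (one subject in 24 is about 4 percentage points) and the corrections are cheap.

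**What to change.** Make two changes to SAP 12.1.6.

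1. Replace the sentence on first occurrence within each timing category with a rule of this kind: for each subject and each level (overall, primary SOC, PT, category of interest), only the first occurrence since the first R788 dose is counted, in the one interval in which it falls. Leave the on-treatment interval denominators unchanged. Restricting them to subjects still free of the event would be a different analysis, and no fault has been shown that calls for it.
2. Define the follow-up denominator as R788-treated subjects who entered a follow-up period, and print that number in the table.

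The cost is two sentences and a small programming change, with no new data.

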### **12.1.7 Occurrence of adverse events and adverse drug reactions by dose at onset**

Applicable period: R788 treatment period

The variables to be analyzed are as follows:

- AEs and ADRs
- AEs and ADRs of interest

For each dose at onset, the number of events, number of subjects with events, and incidence rates of events will be presented overall and by primary SOC and PT. Events occurring during drug interruption will be excluded from the analysis. The denominator for the incidence will be the subjects who received the applicable dose at least once. For AEs and ADRs of interest, event categories will be presented instead of primary SOCs.

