8.6.2.2 Dose adjustment due to adverse events

The dose of the study drug will be adjusted according to the applicable appendices if the following adverse events or abnormal results of laboratory tests, abnormal findings, and abnormal symptoms associated with adverse events are observed.

- Increases in ALT, AST, or bilirubin (see Appendix 3)
- Neutrophil count decreased (see Appendix 4)
- Onset of diarrhea (see Appendix 5)
- Increase in blood pressure (see Appendix 6)

Additionally, if any other severe or serious adverse events with a potential relationship to the study drug are observed, the dose of the study drug should be adjusted at the discretion of the investigator.

If adverse events or abnormal results of laboratory tests, abnormal findings, and abnormal symptoms associated with adverse events which result in dose reduction of study drug recover, the dose of study drug can be re-escalated by 1 dose level in accordance with Table 8.6.2.2-1 based on the investigator's decision.

If adverse events or abnormal results of laboratory tests, abnormal findings, and abnormal symptoms associated with adverse events which leads to interruption of study drug recover, the study drug is restarted at 1 lower dose level than that before the interruption. After restarting the study drug, the dose of study drug can be re-escalated by 1 dose level in accordance with Table 8.6.2.2-1 based on the investigator's decision. The study drug will be restarted at 100 mg qd when the dose regimen before interruption is 100 mg qd. For "2) Recurrence of neutrophil count of < $1000/\mu$ L" in "Appendix 4 Management of Neutrophil Count Decreased" or "3) Recurrence of Grade 3 or 4 diarrhea" in "Appendix 5 Management of Diarrhea," study drug is restarted at 2 lower dose level after the adverse event or laboratory test abnormality, abnormal finding, or symptom associated with the adverse event is recovered. However, the study drug will be restarted at 100 mg qd when the dose before interruption is 100 mg qd or 150 mg qd. The study drug will be administered in the morning when it is administered once daily.

Table 8.6.2.2-1 Dose Adjustment

	Dose re	duction		Dose before	Γ	ose escalatio	n
Dose level -4	Dose level -3	Dose level -2	Dose level	dose increase/ reduction	Dose level +1	Dose level +2	Dose level +3
Interruptio n	100 mg qd	150 mg qd	100 mg bid	150 mg bid	_	_	_
_	Interruptio n	100 mg qd	150 mg qd	100 mg bid	150 mg bid	_	_

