### 5.3 Reporting of Complications, Adverse Events, and Adverse Drug Reactions

Primary System Organ Classes (SOCs) and Preferred Terms (PTs) will be reported according to Medical Dictionary for Regulatory Activities (MedDRA).

For adverse events (AEs) of interest, event categories will be presented instead of primary SOCs. Subcategories will be set and reported for gastrointestinal complaints among AEs of interest. Category-based data summarization will also include subcategory-based summarization.

AEs for which more than one action was taken with the study drug will be reported with the highest level of action taken (discontinuation > dose reduction > interruption).

The definition of AEs of interest is shown in [Table 5.3-1](#).

Table 5.3-1 Adverse Events of Interest

AEs of interest (category)	Applicable PT (PT code)
Bleeding events	Conjunctival haemorrhage (10010719), Epistaxis (10015090), Haemorrhage subcutaneous (10018999), Menorrhagia (10027313), Mouth haemorrhage (10028024), Purpura (10037549), Contusion (10050584), Procedural haemorrhage (10071229)
Gastrointestinal complaints	AEs that fall under the following subcategories:
Nausea	Nausea (10028813)
Vomiting	Vomiting (10047700)
Non-infectious diarrhea SMQ	Diarrhoea (10012735)
Abdominal pain	Abdominal discomfort (10000059), Abdominal pain (10000081), Abdominal pain upper (10000087)
Infection	Cellulitis (10007882), Cystitis (10011781), Diarrhoea infectious (10012742), Diverticulitis (10013538), Gastroenteritis (10017888), Gingivitis (10018292), Herpes zoster (10019974), Nasopharyngitis (10028810), Otitis media (10033078), Paronychia (10034016), Periodontitis (10034539), Pulpitis dental (10037464), Urinary tract infection (10046571), Viral infection (10047461), Tinea infection (10060889), COVID-19 (10084268)
Hypertension SMQ	Blood pressure increased (10005750), Hypertension (10020772)
Neutropenia	Neutropenia (10029354), Neutrophil count decreased (10029366)
Drug related hepatic disorders SMQ	Alanine aminotransferase increased (10001551), Aspartate aminotransferase increased (10003481), Autoimmune hepatitis (10003827), Blood bilirubin increased (10005364), Hepatic cyst (10019646), Hepatic function abnormal (10019670), Hepatic steatosis (10019708), Liver function test abnormal (10024690), Hepatic enzyme increased (10060795), Liver function test increased (10077692)
Thrombosis, embolism, and thromboembolism	Not applicable

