- Elapsed time after administration = Time of blood sampling – Time of study drug administration
- Treatment compliance = Total number of administered tablets / Number of prescribed tablets × 100

- Number of prescribed tablets

Defined as the sum of the products of the number of tablets prescribed per day and the duration of treatment. However, if dose interruption due to an AE or any other reasons occurs during a period other than the non-dosing period, the dose prescribed immediately before the dose interruption will be applied.

- Treatment dose at each analysis visit

Defined as the dose at the time of measurement of platelet count. For Day 1 of Period I, Week 24 of Period II, and Day 1 of Period III, the initial doses for each period will be used. If the study drug is interrupted on the relevant day, the dose will be categorized as interruption. Analysis visits after treatment discontinuation will be excluded from the analysis.

- Average daily dose

Defined as the weighted average of treatment dose, with the duration of exposure at each dose as the weighting factor. Dose interruption will be handled as 0 mg dose.

- Duration of platelet response = End day of response – Start day of response + 1

The start day of response is defined as the first day after the start of study treatment in each period on which a platelet count of  $\geq 50000/\mu\text{L}$  for at least 28 consecutive days without the use of rescue medications was achieved. The end day of response is defined as the day of use of a rescue medication or the first day of the period in which the platelet count fell below  $50000/\mu\text{L}$  for at least 28 consecutive days, whichever is earlier. For subjects who discontinue or complete each period with the platelet count maintained at  $\geq 50000/\mu\text{L}$ , the last measurement day in each period is defined as the end day of response. The calculation of the duration of platelet response includes analysis visits outside the acceptable time window and unscheduled visits.

- Sustained stable platelet response

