## **10.4 Daily Dose**

Applicable period: Period I, long-term treatment of R788, Period II, Period III

- Dose: 100, 150, 200, and 300 mg/day, withdrawal

The numbers and percentages of subjects treated with each dose level will be presented.

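### SAP 12.1.7 reports AE incidence by dose at onset per subject ever on that dose, so unequal time at each dose can create, hide or reverse a dose gradient

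*SAP*

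**What the plan says.** SAP 12.1.7 covers the R788 treatment period. Under SAP 3 item 6 this means Periods I to III for subjects randomised to R788, and Periods II and III for placebo subjects who transition. For each dose at onset it plans event counts, subjects with events and incidence. Events during interruption are left out. The denominator rule is "The denominator for the incidence will be the subjects who received the applicable dose at least once". SAP 16.3 item 12 gives the purpose: "Added to evaluate the impact of the dose on the onset of AEs and ADRs".

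The other planned outputs that bear on time at dose are these:

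- **SAP 10.1 and 10.2** summarise duration of exposure, but not by dose.
- **SAP 10.4**: "The numbers and percentages of subjects treated with each dose level will be presented". SAP 7 defines the treatment dose at a visit: "Defined as the dose at the time of measurement of platelet count". Visits are 2 weeks apart in Period I, 4 in Period II and 8 in Period III. Section 10.4 does not list the R788 treatment period.
- **SAP 10.5** does cover the R788 treatment period and gives average daily dose: "Defined as the weighted average of treatment dose, with the duration of exposure at each dose as the weighting factor". The duration at each dose is therefore already derived, but only as a weight.
- **SAP 11.2.7.1 and 13.1.2** plan individual plots that show each subject's dose.
- **SAP 12.1.5 and 12.1.6** look at timing of events, but not within dose. Section 12.1.5 already uses cut-offs at Day 29 and Day 85.

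**The concern.** A head-count denominator supports a comparison between doses only if subjects spend similar time at each. The protocol makes that unlikely:

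- Period I starts at 100 mg bid, and escalation opens at Week 4 for low platelet counts (8.6.1, 8.6.2.1).
- Adverse events and very high platelet counts move subjects down (8.6.2.2, 8.6.2.3).
- Some subjects last on 150 mg bid begin Period II at 100 mg bid (8.6.1).
- Period III runs until marketing approval (8.2), so follow-up is open-ended and falls on whatever dose the subject has reached.

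A reader who takes the table at its stated purpose could see a dose effect where none exists, or miss one that does. This is the only planned AE table broken down by dose, so nothing else in the safety output would correct that reading.

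**Working it through.** The documents state no AE incidence by dose and no expected time at each dose, so there is no planned figure to reproduce. The following are illustrations.

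**Inputs, all assumed unless noted.** Hazard is 0.01 per week at both doses. All 24 subjects (planned total, Protocol 8.9.1) start R788 at 100 mg bid and are followed for 52 weeks. A share p escalates once to 150 mg bid, with p = 1/2 or 2/3; the rest stay at 100 mg bid. Once-daily doses, dropout and Period III are ignored. F(x) = 1 − exp(−x), where x is cumulative hazard.

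**1. Escalation at Week 4, no dose effect**
- 100 mg bid: p·F(0.04) + (1−p)·F(0.52) = 22.2% (p = 1/2) or 16.1% (p = 2/3).
- 150 mg bid: F(0.48) = 38.1%.
- Ratio: 1.71 or 2.36. In subjects: about 4.6 of 12 v 5.3 of 24, or 6.1 of 16 v 3.9 of 24.
- Person-time at 150 v 100 mg bid: 11.1 v 12.9 patient-years, or 14.8 v 9.2. The event rate is 0.52 per patient-year at both doses, by construction.

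**2. As 1, with escalators back at 100 mg bid in Weeks 24 to 28**
- 100 mg bid: p·F(0.08) + (1−p)·F(0.52) = 24.1% or 18.6%.
- 150 mg bid: F(0.44) = 35.6%.
- Ratio: 1.48 or 1.91.

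**3. Escalation at Week 40, no dose effect**
- 100 mg bid: p·F(0.40) + (1−p)·F(0.52) = 36.8% or 35.5%.
- 150 mg bid: F(0.12) = 11.3%.
- Ratio: 0.31 or 0.32.

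**4. A real effect hidden or reversed**
- Double the hazard at 150 mg bid to 0.02. Twelve weeks there gives F(0.24) = 21.3%, the same as 24 weeks at 100 mg bid, so a true doubling disappears.
- In the Week 40 case the same 21.3% stands against 36.8% or 35.5%, a ratio of 0.58 or 0.60, so the doubling is reversed.

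**5. A rate taken from the documents.** Protocol 1.4.1 reports treatment-related diarrhea in 27 of 102 overseas R788 subjects. If hazard is constant and all were at risk for 24 weeks, it is −ln(1 − 27/102)/24 = 0.0128 per week. With no dose effect, if 25% escalate at Week 12, the incidence by Week 24 is 14.3% at 150 mg bid v 23.4% at 100 mg bid (ratio 0.61). If all escalate at Week 4, it is 45.9% v 5.0% by Week 52 (ratio 9.2).

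**6. Which time bands the remedy needs.** Let events cluster early at either dose: 0.03 per week to Week 4, then 0.01, with escalation at Week 4.
- Crude incidence: 38.1% v p·F(0.12) + (1−p)·F(0.60) = 28.2% or 22.6%; ratio 1.35 or 1.69.
- Overall rate at 100 mg bid: 52·[0.12p + 0.60(1−p)]/[4p + 52(1−p)] = 0.669 or 0.728 per patient-year, v 0.52 at 150 mg bid; ratio 0.78 or 0.71.
- Up to Week 12, 100 mg bid: 52·[0.12p + 0.20(1−p)]/[4p + 12(1−p)] = 1.04 or 1.14, v 0.52; ratio 0.50 or 0.45.
- Weeks 4 to 12, and after Week 12: 0.52 v 0.52.

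A single cut at Week 12 therefore produces its own false gradient. A first cut at Week 4 removes it, because before Week 4 all person-time in this model is at 100 mg bid and there is nothing to compare.

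**The case against.** The strongest reply is that the table is untested, the denominator is openly stated, and the plan is not silent on dose over time. The plots in SAP 11.2.7.1 show every subject's dose by day, and with a planned 24 subjects a reader can follow them. SAP 10.4 allows a rough rate to be built from visit-level counts. This lowers the stakes. It does not answer the point, because plots give no totals, section 10.4 sees only the dose at the platelet measurement, and neither corrects the subject-level percentages.

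A second reply is that the illustration is not this population. That is true. A placebo subject who completes Period I with a Week 24 count of at least 50000/µL keeps the last regimen (Protocol 8.6.1) and so could begin R788 at 150 mg bid. The return to 100 mg bid applies only to some completers, and Period III adds further time. The ratios show that size and direction are not fixed; they do not predict the result.

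A third reply is that person-time does not make the comparison causal. This stands. Non-responders escalate and subjects with adverse events are reduced, so dose remains confounded with response and tolerability.

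A reader might go further and infer that SAP 5.3, which reports an AE with several actions under the highest one and ranks interruption lowest, undercounts AEs leading to interruption. Protocol 8.6.2.2 says that after most AE interruptions "the study drug is restarted at 1 lower dose level than that before the interruption". The documents do not support that inference. Protocol 10.15.6 does not say whether such a restart is also recorded as a dose reduction for the same AE, and Protocol 19.1 leaves CRF completion to a separate procedure. The effect could be nil. The hierarchy is declared, and no AE is lost under it.

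**Conclusion.** The point holds as a limitation of one descriptive safety table. The 12.1.7 percentages mix hazard with time at risk, and no planned table gives total time at each dose. Under the assumed 1% weekly hazard the crude ratio runs from about 0.3 to 2.4 when the true ratio is 1. The actual size and direction cannot be known from the documents. A reader might infer that the table systematically overstates risk at 150 mg bid; the working does not support that, since late escalation pushes the other way. Nothing here touches the primary endpoint, the overall AE counts or any dosing rule. It is a worthwhile improvement rather than a necessary correction.

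**What to change.** In SAP 12.1.7:

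- Keep the crude counts and percentages.
- Add person-time at each dose, excluding interruption days to match the numerator, from the durations already derived for average daily dose.
- Add exposure-adjusted rates per patient-year, for events and for subjects with a first event.
- Show these overall and by time since first R788, with a first cut at Week 4 (Day 29) and a second at Week 12 (Day 85). Do not use a Week 12 cut alone.
- State that dose is not randomised and that the comparison is descriptive.

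The cost is SAP wording and some extra programming; no new data are needed. Downsides: cells will be sparse with about 24 subjects, the rates assume a roughly constant hazard within each band, and confounding by response and tolerability remains. The Week 4 visit window in Period I is Days 26 to 32, so a Day 29 cut will separate pre- and post-escalation time only to within about 3 days for subjects who escalate at that visit.
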